3. STATISTICAL METHODS

3.1. General considerations

Descriptive statistics depending on the nature of the criteria and the number of patients by dose level combinations:

- For **qualitative data**, number of observed values, number and percentage of patients per class will be presented. Unless otherwise specified in the TLG, no class "Missing" is considered.
- For **quantitative data**, number of observed values, mean, standard deviation (SD), minimum (min) and maximum (max), median, first (Q1) and third (Q3) quartiles.

For **Event**:

- Number of patients (or cycles) having experienced the event (n).
- Number of events that occurred (for AE analyses only) (NAE).
- Number of patients (or cycles) at risk for the event (N).
- Global incidence rate (%),
 - o calculated as the ratio between the number of patients (or cycles) having experienced the event (n) and the number of patients (or cycles) at risk at the beginning of the study (N).

Globally, mean, standard deviation and the percentage will be submitted only to the dose level combinations with sufficient number of patients.

3.2. Disposition and baseline characteristics

Description of disposition of patients (status, protocol deviations and analysis set), treatment duration and extent of exposure, as well as other baseline characteristics will be performed by dose level combination and overall.

Calculation rules for general definitions (such as value prior to treatment, under treatment, analysable value, IMP infusion date,...) are provided in [Appendix 4.1](#).

Specific definitions on disposition of patients, baseline characteristics and patient follow-up are provided in [Appendix 4.2](#).

3.2.1. Disposition of patients

Disposition of patients will be described overall for the Screened Set. Number of patients screened, included and not included, with relative reasons, will be presented.

Disposition of patients at the time of inclusion will also be described overall and by planned treatment dose for the IS. Number of patients included, with relative conformity to protocol, and withdrawn, with relative reasons, will be presented.

Furthermore, disposition of patients for the IS will also be described after inclusion, separately for LID period and for each cycle. Number of patients ongoing at the given LID period or cycle, and withdrawn, with relative reasons, will be presented.

3.2.2. Protocol deviations

Protocol deviations before or at inclusion, as well as after inclusion, will be described in the IS, overall and by category of deviations (based on International Conference on Harmonisation (ICH) E3 guideline and ICH E3 Q&A). Number of protocol deviations (NPD), number and percentage of patients with at least one protocol deviation will be presented.

3.2.3. Analysis sets and subgroups

The number of patients in each analysis set (studied analysis set and reference analysis set), and reasons for exclusion will be described.

Listings of patients with their membership, or not, of each analysis set and of excluded patients with reasons for exclusion will be provided.

3.2.4. Demographic data and other baseline characteristics

3.2.4.1. Demographic data

Descriptive summary statistics (n, mean, SD, median, min, max, median, Q1, Q3) will be provided for variables measured on a continuous scale, for patients of the IS:

- Age.

The frequency distribution (n, %) will be provided for patients of the IS by dose level combination and overall for variables measured on a nominal scale for the following classes:

- Age ([18-65[years, [65-85[years, \geq 85 years).
- Gender (Female, Male).
- Race (Caucasian/White, Black/African American, American Indian/Alaska Native, Asian, Native Hawaiian/Other Pacific Islander, Other).
- Ethnicity (Hispanic or Latino, Not Hispanic or Latino).

3.2.4.2. Pregnancy test

The frequency distribution (n, %) will be provided for female patients of the IS by dose level combination and overall for variables measured on a nominal scale for the following cases:

- Pregnancy test (Yes, No).
- Positive pregnancy test (Yes, No).
- Patient childbearing potential (Yes, No).

3.2.4.3. Disease history

Descriptive summary statistics (n, mean, SD, median, min, max, median, Q1, Q3) will be provided for variables measured on a continuous scale for:

- Disease duration (years).
- Treatment-free interval since previous AML treatment line (days).

- Treatment-free interval since previous (MyeloDysplastic Syndrome) MDS treatment line (days).

The frequency distribution (n, %) will be provided in patients of the IS by dose level combination and overall for variables measured on a nominal/ordinal scale according to the following classes:

- Disease duration (≤ 1 years,]1-2 years],]2-4 years] , > 4 years).
- Treatment-free interval since previous AML treatment line (≤ 30 days,]30-60 days], > 60 days).
- Treatment-free interval since previous MDS treatment line (≤ 30 days,]30-60 days], > 60 days).
- Patient with at least one progression during or after a previous treatment line for AML (Yes, No).
- Subtype of AML:
 - AML with recurrent genetic abnormalities.
 - AML with myelodysplasia-related changes.
 - Therapy-related myeloid neoplasms.
 - AML, not otherwise specified.
 - Myeloid sarcoma.
 - Myeloid proliferations related to Down syndrome.
- Disease status (In relapse, Refractory to previous treatment, Treatment-naïve for AML).
- Type of AML (De novo, Secondary).
- FAB: French-American-British (FAB) classification.
- Cytogenetics risk category (Favorable, Intermediate, Intermediate I, Intermediate II, Adverse, Not assessable).
- Red blood cell transfusion dependent (Yes, No).
- Platelets transfusion dependent (Yes, No).
- Presence of myelodysplasia.
- Gene Mutation research at diagnosis (No, Yes).
- List of genes tested (No, Yes).
- Presence of gene mutation (Absent, Present).

A listing of key demographic and disease characteristics will also be presented.

3.2.4.4. Previous therapies

Previous therapies for AML will be summarized for patients in the IS. The following categorical variables will be described by frequency distribution (n, %):

- Number of patients with at least one previous surgery, one previous radiotherapy, one previous drug treatment and one previous transplant.
- Number of patients by combination of previous therapies (drug treatment + radiotherapy, drug treatment + transplant, drug treatment + surgery, radiotherapy + transplant, radiotherapy + surgery, transplant + surgery, drug treatment + radiotherapy + transplant, surgery + radiotherapy + transplant, drug treatment + surgery + radiotherapy, drug treatment + surgery + transplant, drug treatment + surgery + radiotherapy + transplant).
- Number of patients by type of previous transplant (autologous stem cell, allogenic stem cell).
- Number of treatment lines by class (0, 1, 2, 3, 4-7, >7).
- Number of relapses (0, 1, 2, 3, 4-7, >7).

- Number of patients who received some specific treatments lines.
- Previous therapies by pharmacological class.

Descriptive summary statistics (n, mean, SD, median, min, max, median, Q1, Q3) will be provided for variables measured on a continuous scale including:

- Number of treatments lines.
- Number of relapses.

3.2.4.5. Signs and symptoms related to AML

The number and percentage of patients with signs and symptoms at baseline will also be summarized by System Organ Class (SOC) and Preferred Term (PT) in patients of IS.

3.2.4.6. Clinical laboratory baseline evaluation

Laboratory analysis as described in [Section 3.4.4](#) will be analysed in patients of the IS by dose level combination and overall.

For Hepatitis markers B virus surface antigen (HbsAg), B virus surface antibody (HbsAb), B virus core antibody (HbcAb), hepatitis C virus (HCV) RNA-PCR, hepatitis E virus (HEV) RNA-PCR: Descriptive statistics at baseline by classes (negative, positive).

Hepatitis B virus (HBV)-DNA tests: if HbsAg or HbcAb positive at baseline.

3.2.4.7. Initial disease assessments

The frequency distribution (n, %) will be provided in patients of the IS by dose level combination and overall. The following categorical variables will be described by frequency distribution (n, %):

- BM blasts (%)
- BM Auer rods
- Presence of Myelodysplasia
- Neutrophils
- Platelets
- PB Blasts (%)
- Platelets transfusion dependent
- Red blood cells transfusion dependent

3.2.4.8. Medical and surgical history not related to AML

Medical and surgical history other than for the AML will be summarized by SOC and PT according to the Medical Dictionary for Regulatory Activities (MedDRA) dictionary in patients of the IS.

3.2.4.9. Vital signs and clinical examination at baseline

Descriptive summary statistics (n, mean, SD, median, min, max, median, Q1, Q3) will be provided for variables measured on a continuous scale including:

- Weight (kg).
- Height (cm).
- Supine systolic blood pressure (SBP).
- Supine diastolic blood pressure (DBP).
- Supine heart rate (HR).

The frequency distribution (n, %) will be provided in patients of the IS by dose level combination and overall for variables measured on a nominal scale according to the following classes:

- ECOG (0, 1, 2, 3, 4).
- Supine SBP (< 90 mmHg, [90-140 mmHg], ≥ 140 mmHg).
- Supine DBP (< 60 mmHg, [60-90 mmHg], ≥ 90 mmHg).
- Supine HR (< 60 bpm, [60-100 bpm], ≥ 100 bpm).

3.2.4.10. Centralised ECG at baseline

Descriptive summary statistics (n, mean, SD, median, min, max, median, Q1, Q3) will be provided for variables measured on a continuous scale including QT interval (uncorrected) and Fridericia QT interval corrected for heart rate (QTcF).

The frequency distribution (n, %) will be provided in patients of the IS by dose level combination and overall for variables measured on a nominal scale according to the following classes:

- Presence of ECG abnormalities (Yes, No).
- Presence of clinically significant ECG abnormalities (Yes, No).
- QT interval (uncorrected and Fridericia corrected) in classes (≤ 450 ms,]450-480] ms,]480-500] ms and > 500 ms).

3.2.4.11. LVEF at baseline

Descriptive summary statistics (n, mean, SD, median, min, max, median, Q1, Q3) will be provided for LVEF. The frequency distribution (n, %) will also be provided in patients of the IS by dose level combination and overall, according to the following classes:

- LVEF (< 50%, [50-70%], >70%).

3.2.4.12. Chest X-Ray

The frequency distribution (n, %) will be provided in patients of the IS by dose level combination and overall for Chest X-Ray, according to the following classes:

- Chest X-Ray performed (Yes, No).

3.2.4.13. TLS prevention

All concomitant treatments for TLS prevention taken at inclusion and before the treatment period will be described for each dose level combination and overall in the SS, by Anatomical Therapeutic Chemical (ATC) code into 4 levels (Pharmacological class, Pharmacological subclass, therapeutic class, Preferred name). TLS risk category, type of hydration performed and anti-hyperuricaemic administration will also be presented.

3.2.5. Treatments of patients

3.2.5.1. Extent of treatment exposure and treatment compliance

Details concerning definition on extent of exposure, treatment compliance are provided in [Appendix 4.2.1.5](#).

For S64315 and azacitidine separately the frequency distribution (n, %) or descriptive summary statistics (n, mean, SD, median, min, max, median, Q1, Q3) as applicable will be provided in

patients of the SS by planned dose level combination and overall for variables measured on a nominal scale according to the following classes:

- Extent of exposure*:
 - The global treatment duration (combined measure for S64315/azacitidine): summary statistics.
 - Treatment duration (weeks) overall and by treatment period (LID/Combination treatment).
 - Treatment duration (weeks) during combination treatment period (i.e., excluding LID) (< 4 weeks, [4-12[weeks, [12-24[weeks, [24-36[weeks, [36-48] weeks, >48 weeks).
 - LID duration ([0-1] week, [1-2] weeks and > 2 weeks).
 - Number of cycles (1 cycle, 2 cycles, 3-6 cycles, 7-10 cycles, > 10 cycles) during the combined treatment period.
 - Number of patients by cycle (LID, Cycle 1, Cycle 2, etc).
- Treatment compliance*:
 - Cumulative dose (mg) for S64315/ Cumulative dose (mg/m²) for azacitidine overall, by cycle (including LID), and for combination treatment.
 - Dose intensity (DI) (mg/week) for S64315/ DI (mg/m²/day) for azacitidine overall, by cycle (including LID), and for combination treatment.
 - Relative Dose Intensity (RDI) (%) for S64315/azacitidine overall, by cycle (including LID), and for combination treatment.
 - RDI for S64315(< 35%, [35-65[%, [65-100[%, ≥ 100%) overall, by cycle, and per treatment period (LID/Combination treatment).
 - RDI for azacitidine (< 62%, [62-85[%, [85-100[%, ≥ 100%) overall, by cycle, and per treatment period (Combination treatment).
 - Treatment interruption (Yes/No) during treatment period (including LID).
 - Reason of treatment interruption (Medical reason, Non-medical reason, Missing).
 - LIDLIDNumber of cycles with at least one treatment interruption for S64315 during treatment period (including LID).
 - Number of cycles with at least one treatment interruption for azacitidine during treatment period.
 - Cycle delayed (Yes/No) during treatment period (including LID).
 - Reason for cycle delayed (Medical reason, Non-medical reason, Missing).
 - Number of cycles delayed during treatment period (including LID).
 - Number of cycles delayed (1, 2, > 2) during treatment period (including LID).
- Specifically for S64315, the summary of treatment compliance will also will include:
 - Dose modified (Yes/No) during treatment period (including LID).
 - Number of dose modifications during treatment period (including LID).
 - Number of dose modifications (1, 2, > 2) during treatment period (including LID).
 - Time to first dose modification (days) during treatment period (including LID).
 - Partial dose administered (Yes/No) during treatment period (including LID).

- Number of cycles with partial dose for S64315 during treatment period (including LID).
- Number of cycles with partial dose for S64315 (1, 2, > 2) during treatment period (including LID).
- Specifically for azacitidine, the summary of extent of exposure will include:
 - Average number of days dosed per cycle with planned dose level for azacitidine overall.
 - Average number of days dosed overall.
 - Number of azacitidine interruption days.

* Applicable for both S64315 and azacitidine if not specified.

3.2.5.2. Concomitant treatments

Details concerning definition on concomitant treatments are provided in [Appendix 4.2.1.6](#).

All concomitant treatments taken during the study period will be described for each administered dose level combination, and overall, in the SS, by ATC code into 4 levels (pharmacological class, pharmacological sub-class, therapeutic class and preferred name) and into 1 level (pharmacological class only). Concomitant treatments only during the study period are described because we will have an abbreviated CSR for the CL1-64315-004.

3.2.6. Other observations related to patient follow-up

We will have an abbreviated CSR for the CL1-64315-004, therefore, follow-up analysis is not applicable.

3.3. Efficacy analysis

We will have an abbreviated CSR for the CL1-64315-004, therefore, efficacy analysis is not applicable.

3.4. Safety endpoints

All safety analyses will be performed in the SS (resp. DLTES for DLT analysis) by treatment dose level combination and overall. The treatment period is defined from first IMP intake up to last IMP intake date + (*) days.

(*) 30 days for AE and death analysis, 28 days for clinical laboratory evaluation, vital signs and clinical examination, centralized ECG and LVEF analysis.

Qualitative data will be presented in number and percentage of patients per class, while quantitative data will be presented in mean, SD, min and max, median, Q1 and Q3.

Calculation rules for expressions of safety endpoints, as well as general definitions (such as value prior to treatment / under treatment, analysable value, first and last IMP intake dates...), are provided in [Appendix 4.1](#).

Calculation rules for safety endpoints and other specific definitions are provided in [Appendix 4.2](#).

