4.1.3.2. Dose administration schedules

The initial schedule will consist of a 2-week S64315 lead-in dose period followed by a 28-day cycle with the combination, i.e. a weekly regimen for S64315 and a daily regimen for azacitidine over 7 days.

Alternative dosing schedules based on the observed clinical safety, PK/PD data and non-clinical data (in vitro, in vivo, PK/PD modelling data) may be further explored. They should be integrated in the protocol via an amendment.

S64315 will be administered via intravenous (IV) infusion over at least 2h once every week, as follows:

- **2-week lead-in dose period** i.e. fixed lead-in dose 1 (LID1) of 25 mg on D-13 and fixed lead-in dose 2 (LID2) of 50 mg on D-6
- followed by the **combination treatment period over 28-day cycles**, i.e. on CxD2, CxD9, CxD16 and CxD23

The starting dose will be 50 mg. A panel of dose from 25 mg (-1) and up to 250 mg could be explored according to the dose escalation process of the BLRM. For more details, please refer to [Table \(4.1.3.3\) 1](#).

A minimum of 5 days between two infusions of S64315 is required.

An infusion could be postponed in case of 1-day delay and should be discussed with the Sponsor in case of 2-day delay, for any reason other than medical / toxicity.

Azacitidine will be administered during the combination treatment period at 75 mg/m² via subcutaneous (SC) injection, daily for 7 days, i.e. from CxD1 to CxD7, followed by a rest period of 21 days (28-day cycle).

On days of concomitant administration of S64315 and azacitidine (CxD2), azacitidine should be administered 2h (\pm 10 min) prior to S64315.

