4.1.3.6. DLT management

Study treatments must be delayed for any patient who experienced a DLT. Conditions to resume treatment are described in [section 8.12](#).

All DLT will be reported to I.R.I.S. within 24h via the DLT form in the electronic Case Report Form (eCRF). The eCRF ‘Adverse Event’ page should then be filled in, without waiting for the results of the clinical outcome or of additional investigations. When data of the DLT form are submitted, an e-mail will be immediately and automatically sent to the sponsor.

If the eCRF is unavailable when the investigator is informed of the DLT, he/she should:

- report the DLT on a paper ‘DLT form’
- send the form by fax immediately to I.R.I.S. at the following number: [contact]

As soon as the eCRF becomes available again, the investigator must enter the data in the eCRF.

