If the patient is benefiting from the study treatment according to the investigator's judgement and if it is in the patient's best interest to continue the combination of S64315 with azacitidine, the patient may remain on study treatment. A patient must discontinue the combination if the toxicity recurs with the same or worse severity after resumption of dosing, unless the investigator decides it is in the patient's best interest to continue the combination of IMPs and upon documented agreement with the Sponsor.

If one IMP is permanently discontinued, both drugs should be permanently discontinued. A patient must be withdrawn from the study if one the IMPs is interrupted for more than 28 consecutive days from C1D2, for any reason. However, for patients with LVEF decline, IMP interruptions of up to 35 consecutive days are permitted.

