Grade 2	Maintain dose level but initiate/intensify appropriate skin toxicity therapy (e.g. antihistamines, topical corticosteroids and low-dose systemic corticosteroids) as per local institutional guidelines and monitor closely Consider skin biopsy for evaluation
Grade 3, despite skin toxicity therapy	Omit dose and reassess the patient weekly until resolved to Grade \leq 1, then: 
 - If resolved in \leq 14 days, \downarrow 1 dose level - If resolved in $>$ 14 days, discontinue patient form test drug treatment Consider referral to dermatologist and manage rash per dermatologist's recommendations Consider skin biopsy for evaluation

Grade 4, despite skin toxicity therapy	Discontinue patient from study treatment Consider referral to dermatologist and manage rash per dermatologist's recommendations Consider skin biopsy for evaluation
Cardiac disorders	
QTcF Prolongation	
QTcF interval \geq 481ms or increase of $>$ 60 ms from baseline on at least two separate ECG	Omit S64315 dose, correct the possible electrolytes abnormalities (e.g. potassium, magnesium, etc.) and perform frequent ECGs* until resolves to Grade \leq 1, then: 
 - If resolved in \leq 14 days, \downarrow 1 dose level. Triplicate ECGs must be monitored on D1 of each cycle throughout the study - If resolved in $>$ 14 days, discontinue patient from test drug treatment *Perform at least weekly ECGs until 2 weeks following resolution of the QTc prolongation
LVEF Decrease	
Asymptomatic, absolute decrease in LVEF of 10% or greater from baseline and LVEF $<$ 50%	Omit dose, obtain consultation with a cardiologist, and repeat cardiac imaging after 4 weeks 
 - If improved to \leq 10% from baseline and \geq 50% within 4 weeks, then \downarrow 1 dose level. Monitor LVEF on D1 of each subsequent cycle for at least 3 cycles; if no recurrence of LVEF decline and if agreed by the cardiologist, the frequency may then be decreased to every other cycle. - If not improved to \leq 10% from baseline and \geq 50% within 4 weeks, then discontinue patient from test drug treatment
Absolute decrease in LVEF of 20% or greater from baseline and LVEF $<$ 40% OR Symptomatic congestive heart failure	Discontinue patient from test drug treatment and obtain consultation with a cardiologist

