4.1.2. First and last IMP intakes dates

For patients having taken at least one dose of IMP (S64315 or azacitidine), the dates of first and last IMP (S64315 or azacitidine) intake on the analysis period (including LID) will be defined as follows:

- The date of the first IMP intake within the analysis period (including LID).
- The date of the last IMP intake within the analysis period (including LID):
max(last intake date of last cycle of S64315, last intake date of last cycle of azacitidine).

Note: For azacitidine, cycles with both missing first and last IMP intake dates and with administered dose missing or equal to 0 will not be taken into account.

After selection of the dates of first and last IMP intake as defined above, if these dates are missing or incomplete, the following substitution rules will be applied:

Table (4.1.2) 1 - Substitution rules of IMP intake dates

Date to substitute	Substituted date
First IMP (S64315 or azacitidine) intake	
./mmm/yyyy
 
Inclusion date if complete with same month and year Otherwise: 01/mmm/yyyy
 
./.../yyyy
 
Inclusion date if complete with same year Otherwise: 01/JAN/yyyy
 
./.../....
 
Inclusion date if complete

Last IMP (S64315 or azacitidine) intake	
./mmm/yyyy
 
Last available date* if same month and year Otherwise: Last day of the month/mmm/yyyy
 
./.../yyyy
 
Last available date* if same year Otherwise: 31/DEC/yyyy
 
./.../....
 
Last available date* Last available date**

Notes:

- Missing dates will be substituted only for patients having taken at least one dose of study treatment:
./mmm/yyyy = missing day.
./.../yyyy = missing day and month.
./.../.... = totally missing date.
***** Last available date (only for patients included) is defined as date of death if patient died, and as maximum date among completed dates relative to patient's information otherwise.

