4.1.3. Value prior to treatment / under treatment

Table (4.1.3) 1 - Time frame

Criteria	Value prior to treatment if measured between (D1=) days before and (D2=) days after the first IMP intake (D1 and D2 included)		Post-baseline value on treatment period if measured between (D1=) days after the first IMP intake and until (D2=) days after the last IMP intake (D1 and D2 included)	
	D1 =	D2 =	D1 =	D2 =
Disease assessment	D1 = 21	D2 = Xsup	D1 = Xinf	D2 = 28
Biochemistry / haematology / thyroid function / coagulation / hepatitis markers	D1 = 21	D2 = Xsup	D1 = Xinf	D2 = 28
Vital signs	D1 = 21	D2 = Xsup	D1 = Xinf	D2 = 28
ECG/LVEF	D1 = 21	D2 = Xsup	D1 = Xinf	D2 = 28
Pregnancy Test	D1 = 21	D2 = Xsup	D1 = Xinf	D2 = 28
All other criteria (death and AE excepted)	D1 = 28	D2 = Xsup	D1 = Xinf	D2 = 28*

Xsup: 0 and "Visit < "***".

Xinf: 0 and "Visit ≥ "***".

(*): 30 days for AE and death analysis.

(**) Visit number depending on the panel

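### When both drugs are held for an LVEF fall judged a DLT, the 4-week repeat scan falls at day 32-34, outside the SAP's 28-day LVEF window, so further decline in a patient who does not recover is not summarised

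*SAP*

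**What the plan says.** **SAP.** Section 3.4 sets the safety window: "The treatment period is defined from first IMP intake up to last IMP intake date + (*) days". The added days are 30 for AEs and deaths, and "28 days for clinical laboratory evaluation, vital signs and clinical examination, centralized ECG and LVEF analysis". Table (4.1.3) 1 repeats the rule with D2 = 28 in the ECG/LVEF row, under the column headed "Post-baseline value on treatment period if measured between (D1=) days after the first IMP intake and until (D2=) days after the last IMP intake". Section 4.1.2 dates the last intake as the later of the two drugs: "max(last intake date of last cycle of S64315, last intake date of last cycle of azacitidine". Section 3.4.7 then reports the lowest LVEF under treatment, its change from baseline and its CTCAE grade. Section 4.2.3.2 takes the worst AE severity up to last intake + 30 days.

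**Protocol.** S64315 is given weekly, "i.e. on CxD2, CxD9, CxD16 and CxD23" (4.1.3.2). From cycle 2, LVEF scans are on day 1 before dosing or up to 2 days earlier, every cycle at first and every second cycle from cycle 4 (8.2.2). For an asymptomatic fall of at least 10 points to below 50%, Table (8.12) 1 omits the dose and asks sites to "repeat cardiac imaging after 4 weeks". A patient who has not improved is discontinued. The same fall is a DLT criterion in Table (4.1.3.5) 1, and 4.1.3.6 states: "Study treatments must be delayed for any patient who experienced a DLT". Section 5.8.1 relaxes the general 28-day limit on interruptions: "for patients with LVEF decline, IMP interruptions of up to 35 consecutive days are permitted".

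**The concern.** The protocol makes room for an interruption longer than 28 days when LVEF has fallen, but the SAP's LVEF window was left at 28 days. The scan that decides whether the patient continues can therefore fall outside the analysis. Whether it does depends on its result. Recovery leads to redosing, which moves the last-intake date forward and brings the scan back in. Non-recovery leads to discontinuation, which fixes the last-intake date and leaves the scan out.

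The stakes are specific to this drug. Protocol 2.2.2 reports cardiotoxicity as the dose-limiting toxicity of S64315 alone, and SAP 1.2 lists LVEF among the endpoints for the primary objective. With up to 30 patients planned in the escalation part, one patient placed in the wrong grade is visible in the tables.

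**Working it through.** The plan has no calculated figure to reproduce. The check is calendar arithmetic, with absolute day = 28 × (cycle − 1) + day.

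**Inputs**
- Last S64315 dose before the scan: C1D23 = day 23 (Protocol 4.1.3.2).
- Scheduled scan: C2D1 = day 29, or up to 2 days earlier, so day 27-29 (Protocol 8.2.2).
- Repeat scan: 4 weeks, taken as 28 days, after detection (Table (8.12) 1).
- Cut-offs after last intake: LVEF 28 days, AE severity 30 days (SAP 3.4 and 4.2.3.2).

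**Case A: both drugs held after D23**
- Detection: 27 − 23 = 4 to 29 − 23 = 6 days after the last dose.
- Repeat: 4 + 28 = 32 to 6 + 28 = 34 days after the last dose.
- Overrun of the LVEF window: 32 − 28 = 4 to 34 − 28 = 6 days.
- Overrun of the AE severity window: 32 − 30 = 2 to 34 − 30 = 4 days.
- Later cycles give the same spacing: C4D1 is day 85 and C3D23 is day 79, so detection is at 6 and repeat at 34.
- An unscheduled scan k days after the last dose gives a repeat at k + 28, outside the LVEF window for every k of 1 or more.
- If D23 was missed and the last dose was D16, the repeat is at (27 + 28) − 16 = 39 to (29 + 28) − 16 = 41 days.

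**Case B: S64315 omitted, azacitidine given on C2D1-D7**
- Last intake: C2D7 = day 35.
- Repeat: 55 − 35 = 20 to 57 − 35 = 22 days after the last intake (22-24 if azacitidine ended on D5). This is inside the window whether or not LVEF recovered.

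**Check against the 35-day allowance.** C1D23 to C3D2 is 58 − 23 = 35 days, so the protocol's allowance fits one omitted cycle with restart on D2 of the next.

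**Effect on the summary in Case A, no recovery** (illustrative values, graded by SAP 4.2.3.5.3)

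| | LVEF | Change from 60% | Value class | Grade |
|---|---|---|---|---|
| Detection (counted) | 48% | 48 − 60 = −12 | 40 to below 50 | 2 |
| Repeat (not counted) | 35% | 35 − 60 = −25 | below 40 | 3 |

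The table would show Grade 2 and −12. If the repeat were stable at 48%, nothing would change. If LVEF had recovered, the counted repeat would by rule be at least 50%, above the value at detection, and could not alter a lowest-value summary.

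**The case against.** The strongest reply concerns azacitidine. Table (8.12) 1 governs S64315 and names azacitidine separately where it is meant, as in the myelosuppression row. Section 8.12 requires both drugs to stop when S64315 is discontinued, not when a dose is omitted. Other sections allow for interrupting one drug alone. Because the SAP window runs from the later drug, continued azacitidine puts the repeat scan inside it. This stands, and it limits the point to Case A. It does not remove Case A: the LVEF trigger is also a DLT criterion, 4.1.3.6 delays study treatments after a DLT, and the legend to Figure (4.1.1) 1 lists both drugs under that term. Case A therefore needs the investigator to judge the fall related to S64315, since relatedness is part of the DLT definition.

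Three further replies also stand. The first fall is always counted, at Grade 2 or worse. Under SAP 4.2.3.2 a late episode of an emergent AE that leads to withdrawal is still counted as such, and seriousness is judged on the whole event, so only the worst AE grade is cut short. The table and listing shells are in a separate document, so a listing of later LVEF values cannot be ruled out.

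A reader might go further and infer that the repeat scan counts only for patients who recover and are redosed. Case B contradicts that. A reader might also infer that anyone withdrawn after an interruption of more than 28 days has a withdrawal visit outside the window. That fails when the other drug continued, because the withdrawal rule is triggered by interruption of either one. Nor do the documents show a matching repeat-assessment problem for ECG or laboratory data.

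**Conclusion.** The point holds in conditional form. When the fall is judged a DLT, both drugs are held after D23 and the patient does not recover, the on-schedule repeat scan misses the LVEF window by 4-6 days and the AE severity window by 2-4 days. What can be lost is further decline between detection and repeat, or in later monitoring. The error runs one way, toward understating the depth of the fall. The event itself, the DLT count and attribution of the withdrawal are not lost.

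This assumes a repeat 28 days after detection. A repeat made no more than 22-24 days after detection (28 − 6 to 28 − 4) would still count. The documents give no frequency for this sequence. Few patients are likely to be affected, and the report is descriptive and abbreviated, with escalation already stopped. The correction is still worth making, because it concerns the known dose-limiting organ and a primary-objective endpoint.

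**What to change.** In SAP 3.4 and in the ECG/LVEF row of Table (4.1.3) 1, separate LVEF from ECG. For LVEF only, do one of the following:
- extend the on-treatment window to at least last IMP intake + 35 days, which covers day 32-34 and matches the interruption the protocol permits for LVEF decline; or
- extend it to include the repeat scan made to resolve the LVEF hold. This also covers the day 39-41 case after a missed D23 dose, which a fixed 35 days does not.

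In SAP 4.2.3.2, take the worst grade of an LVEF-decrease AE already ongoing over the same window. List any LVEF values recorded later. Leave the ECG and laboratory windows as they are, since a general extension could admit values obtained after other anti-leukaemic therapy has started.

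The cost is SAP wording and one derivation. No new data are needed and nothing changes for patients. The downside is that a few late LVEF values unrelated to treatment may enter the summary.
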